4.4 Method of assignment to substudy and treatment

Patients will be assigned to a specific substudy based on the appropriate eligibility criteria.

For all substudies, a unique enrollment code will be assigned after written informed consent has been obtained, using the centralized Interactive Web Response System (IWRS). If a patient withdraws from participation in the study, his or her enrollment code will not be reused.

4.4.1 Substudy 1

All eligible patients will receive derazantinib 300 mg QD monotherapy. Treatment assignment is performed on C1D1, or as close as possible to the date on which treatment is to be administered.

4.4.2 Substudy 3

All eligible patients will receive derazantinib 200 mg BID and atezolizumab 1200 mg Q3W in combination. If derazantinib 200 mg BID at the safety interim analysis is not assessed as safe and tolerable, patients will be treated with the RP2D determined in Substudy 2 (i.e., derazantinib 300 mg QD and atezolizumab 1200 mg Q3W in combination). Treatment assignment is done on C1D1, or as close as possible to the date on which treatment is to be administered.

4.4.3 Substudy 4

Patients in **Substudy 4** are to be randomized (1:1) to receive study treatment with either derazantinib 300 mg QD monotherapy (**Cohort 4a**), or derazantinib 300 mg QD and atezolizumab 1200 mg Q3W in combination (**Cohort 4b**), based on a computer-generated randomization schedule via IWRS. Patients in Substudy 4 will be randomized on C1D1, or as close as possible to the date on which treatment is allocated. Randomization will be stratified for key prognostic factors according to the following algorithms:

- The presence of visceral metastasis, an ECOG PS of 2, or a preceding FGFR inhibitor treatment interval of less than 6 months (i.e., less than 24 full weeks) will be credited with one point, and patients will be stratified according to their composite score values of 0–1 versus 2–3 points.

4.4.4 Substudy 5

All eligible patients will receive derazantinib 200 mg BID monotherapy. Treatment assignment is performed on C1D1, or as close as possible to the date on which treatment is to be administered.

4.5 Discontinuation from the study treatment or study

4.5.1 Patient discontinuation from study treatment

Patients should be discontinued from study treatment at any time if they experience documented radiographic progression of disease. Patients will be permitted to remain on study treatment after RECIST 1.1 criteria for PD are met **only** if, in the opinion of the Investigator and with the agreement of the Medical Monitor, they continue to derive benefit from derazantinib or derazantinib-atezolizumab in combination.

In particular, for patients in **Cohort 4a**, every effort should be undertaken to obtain BICR confirmation on disease progression, in order to establish a baseline for a potential crossover.

Furthermore, patients should be discontinued from study treatment should any of the following occur:

- Any clinically unacceptable treatment-emergent toxicity occurring in patients treated with derazantinib monotherapy that persist despite optimal treatment or dose reduction
- Any clinically unacceptable treatment-emergent toxicity clearly attributable to derazantinib occurring in patients treated with derazantinib-atezolizumab in combination that persist despite optimal treatment or derazantinib dose reduction. In this instance derazantinib should be discontinued, whilst continuation of atezolizumab is at the discretion of the Investigator
- Any clinically unacceptable treatment-emergent toxicity clearly attributable to atezolizumab occurring in patients treated with derazantinib and atezolizumab in combination that require respective management, as detailed in [Appendix 4](#)
- Both study drugs (derazantinib and atezolizumab) should be discontinued for instances of overlapping toxicity (e.g., ophthalmological and/or hepatic adverse events) that cannot be clearly attributed to either drug
- Pregnancy (see Section [7.4.5](#))
- Patient decision to discontinue treatment and study visits
- Withdrawal of consent from treatment and study follow up calls
- Non-compliance with any part of the study, as assessed by the Investigator or Medical Monitor
- Investigator's decision after discussion with the Medical Monitor or designee
- Death

For all patients who discontinue derazantinib, AE monitoring must be continued for at least 28 days after the last dose of study drug (see Section 5.2.2.8); for patients discontinuing atezolizumab, AE monitoring must be continued for at least 90 days after the last dose (see Section 5.2.2.9).

For patients who fail to return for the End of Treatment visit and/or the Safety Follow-up visit(s), the Investigator must make every effort to contact the patient (by telephone or mail correspondence). The outcome of this contact must be documented by the Investigator and filed in the Investigator Site File (ISF). The reasons for discontinuation of treatment must be recorded in the eCRF.

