> 10.0 mg/dL (> 3.23 mmol/L) or significant alteration from baseline renal function or Grade 3 hypercalcemia	Withhold derazantinib with weekly reassessments until the level returns to < 5.6 mg/dL; the patient may restart at two dose levels lower, or permanently discontinue derazantinib (e.g., if considered life threatening event).
Central serious retinopathy / Retinal pigment epithelial detachment	
Grade	Action
Asymptomatic clinical or diagnostic observations only (Grade 1)	Withhold derazantinib until resolution. If the event resolves within 4 weeks, restart at the next lower dose level. If stable but not resolved for two consecutive eye examinations, restart at the next lower dose level.
Visual acuity 20/40 or better or ≤ 3 lines of decreased vision from baseline (Grade 2)	Withhold derazantinib until resolution. If the event resolves within 4 weeks, the patient may restart at the next lower dose level.
Visual acuity worse than 20/40 or > 3 lines of decreased vision from baseline (Grade 3)	Withhold derazantinib until resolution. If the event resolves within 4 weeks, the patient may restart at two dose levels lower. If the event recurs, consider permanent discontinuation of derazantinib.
Visual acuity 20/200 or worse in affected eye (Grade 4)	Permanently discontinue derazantinib.
Other events	
CTCAE grade	Action
Grade 1 or 2	Continue derazantinib at current dose, unless dose delay/modification may be clinically indicated (as assessed by the Investigator and agreed upon by the Medical Monitor or designee).
Grade 3	Withhold derazantinib until recovery to Grade 1 or baseline; administer derazantinib at the next lower dose for subsequent dosing, unless further dose reduction is required.
Grade 4	Permanently discontinue derazantinib if the event is at least possibly related to derazantinib.

Abbreviations: CTCAE, Common Terminology Criteria for Adverse Events.

6.1.1.5.1 *Hyperphosphatemia*

For all patients, it is recommended to restrict phosphate intake to 600–800 mg daily. As hyperphosphatemia is only defined by NCI CTCAE 5.0 with regards to escalating interventional measures (without specifications triggering these interventions) and not by laboratory values exceeding the upper limits of normal leading to specific interventions, [Table 5](#) guides interventions for the management of hyperphosphatemia considered at least possibly related to derazantinib.

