6.1.2.6 Dose modifications

Dose modifications/reductions of atezolizumab are not permitted. Patients treated with derazantinib and atezolizumab in combination should be temporarily or permanently discontinued from atezolizumab and/or study treatment if any of the toxicities described in [Appendix 4](#) occur, and are assessed by the Investigator as at least possibly atezolizumab-related.

If atezolizumab is discontinued per these guidelines, continuation of derazantinib is at the discretion of the Investigator (see [Section 4.5.1](#)).

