Appendix 4 Management of atezolizumab-specific adverse events

Note: This appendix is a redacted version of the detailed guidance for the management of immune-related AEs, located in the atezolizumab IB (Edition 17), which should be consulted for further guidance.

Pulmonary events including pneumonitis	
Event	Management
Grade 1	Continue atezolizumab and monitor closely.
Grade 2	
 Withhold atezolizumab for up to 12 weeks after event onset. Refer patient to pulmonary and infectious disease specialists and consider bronchoscopy or bronchoscopic alveolar lavage. Initiate treatment with corticosteroids equivalent to 1-2 mg/kg/day oral prednisone. If event resolves to Grade 1 or better, resume atezolizumab. If event does not resolve to Grade 1, permanently discontinue atezolizumab and contact Medical Monitor. For recurrent events, treat as a Grade 3 or 4 event.
Grade 3 or 4	
 Permanently discontinue atezolizumab and contact Medical Monitor. Bronchoscopy or bronchoscopic alveolar lavage is recommended. Initiate treatment with corticosteroids equivalent to 1-2 mg/kg/day oral prednisone, and consider adding an immunosuppressive agent if event does not improve within 48 hours after initiating corticosteroids. If event resolves to Grade 1 or better, taper corticosteroids over ≥ 1 month.

Hepatic events	
Event	Management
Grade 1	Continue atezolizumab and monitor liver function tests (LFTs) until values resolve to normal or to baseline values.
Grade 2	
All events:
 
 Monitor LFTs more frequently until return to baseline values. 
Events with a duration of > 5 days
 
 Withhold atezolizumab for up to 12 weeks after event onset. Initiate treatment with corticosteroids equivalent to 1-2 mg/kg/day oral prednisone. If event resolves to Grade 1 or better, resume atezolizumab. If event does not resolve to Grade 1, permanently discontinue atezolizumab and contact Medical Monitor.

Hepatic events	
Event	Management

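### For hepatic or ocular events that cannot be attributed to one drug, section 4.5.1 and the dose-modification rules give different instructions: derazantinib at Grades 1–3, atezolizumab at Grades 1–2

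*Protocol*

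**What the plan says.** Protocol section 4.5.1 sorts toxicity grounds for stopping by attribution. For combination patients the derazantinib bullet covers "Any clinically unacceptable treatment-emergent toxicity clearly attributable to derazantinib occurring in patients treated with derazantinib-atezolizumab in combination that persist despite optimal treatment" or a derazantinib dose reduction. The atezolizumab bullet is also limited to clinically unacceptable toxicity and refers to Appendix 4. The last toxicity bullet says "Both study drugs (derazantinib and atezolizumab) should be discontinued for instances of overlapping toxicity (e.g., ophthalmological and/or hepatic adverse events"), and its trigger is "overlapping toxicity (e.g., ophthalmological and/or hepatic adverse events) that cannot be clearly attributed to either drug". It carries neither limit.

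Three other places cover the same kinds of event:

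- **Section 6.1.1.5 and Table 5 (derazantinib)** apply to adverse events of special interest and to other events at least possibly related to derazantinib. Hepatic events fall under other events. At Grade 1 or 2 the action is "Continue derazantinib at current dose, unless dose delay/modification may be clinically indicated". At Grade 3 it is "Withhold derazantinib until recovery to Grade 1 or baseline; administer derazantinib at the next lower dose for subsequent dosing". Retinal events have their own rows.
- **Appendix 4 (atezolizumab)** has hepatic and ocular tables. For hepatic Grade 1 the action is "Continue atezolizumab and monitor liver function tests (LFTs) until values resolve to normal or to baseline values".
- **Section 6.1.2.6** applies Appendix 4 to events at least possibly related to atezolizumab, and adds "If atezolizumab is discontinued per these guidelines, continuation of derazantinib is at the discretion of the Investigator", with a reference back to section 4.5.1.

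Section 3.1.4 defines a related toxicity as one possibly or probably related to either drug or to both.

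**The concern.** An event that cannot be pinned on one drug will normally be rated at least possibly related to each. It then meets the section 4.5.1 trigger, the Table 5 trigger and the 6.1.2.6 trigger together. Neither Table 5 nor Appendix 4 exempts overlapping toxicity, and nothing ranks the passages.

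The overlap is foreseeable. Section 1.5.1 names transaminase elevation as derazantinib's important identified risk and ocular disorders as an important potential risk. Section 1.5.2 lists hepatitis/transaminitis among reported atezolizumab effects. Complete eye examinations with optical coherence tomography are scheduled at Day 1 of Cycles 2–5.

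Two things are at stake. One is safety: a patient for whom both drugs were meant to stop may be continued or re-treated, or the reverse. The other is the analysis. Under section 5.2.2.7 the End of Treatment visit follows permanent discontinuation of all study drugs, so the passage a site follows can decide whether a patient reaches that point. SAP section 6.3.2.3 then censors progression-free survival at the last scan before end of treatment when treatment stopped without progression.

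**Working it through.** The plan gives no figure to reproduce here, so the check sets the passages side by side. It takes a combination patient with an event that cannot be clearly attributed and is rated possibly related to both drugs. In every row section 4.5.1 says to discontinue both.

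| Event | Derazantinib, Protocol Table 5 | Atezolizumab, Appendix 4 | Consistent with 4.5.1? |
|---|---|---|---|
| Hepatic, Grade 1 | Continue | Continue, monitor | Neither drug |
| Hepatic, Grade 2 | Continue | Monitor; if longer than 5 days, withhold up to 12 weeks, resume at Grade 1 or better | Neither drug |
| Hepatic, Grade 3 | Withhold, then next lower dose | Permanently discontinue | Atezolizumab only |
| Hepatic, Grade 4 | Permanently discontinue | Permanently discontinue | Both |
| Retinal, Grade 1 | Withhold; restart one level lower, also if stable but unresolved at two examinations | Continue | Neither drug |
| Retinal, Grade 2 | Withhold; may restart one level lower if resolved within 4 weeks | Withhold up to 12 weeks, resume at Grade 1 or better | Neither drug |
| Retinal, Grade 3 | Withhold; may restart two levels lower if resolved within 4 weeks | Permanently discontinue | Atezolizumab only |
| Retinal, Grade 4 | Permanently discontinue | Permanently discontinue | Both |

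Ocular events that are not retinal fall under other events in Table 5 and follow the hepatic derazantinib column.

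**Count.** Two event types, four grades and two drugs give 2 × 4 × 2 = 16 instructions. Derazantinib differs from 4.5.1 at three grades and atezolizumab at two, so 2 × (3 + 2) = 10 of 16 differ and 6 agree.

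**Meaning of discontinued.** The table takes the word in 4.5.1 as permanent. Section 6.1.2.6 speaks of both temporary and permanent discontinuation, so the word alone does not settle it. If a temporary stop were meant, some of the withhold rows could be reconciled with 4.5.1, but the continue rows could not.

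**Reading a threshold into 4.5.1.** All three preceding toxicity bullets require clinically unacceptable toxicity. If the fourth is read the same way, most of the Grade 1–2 conflict weakens. A Grade 3 hepatic event, or a Grade 2–3 retinal event, can still be clinically unacceptable. For derazantinib those events leave a stop in 4.5.1 against withholding and restarting lower in Table 5. Only the further condition of persistence despite treatment or dose reduction would remove that. The two derazantinib bullets carry this condition and the atezolizumab bullet does not, so it is not common to the set and cannot be assumed.

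**The case against.** The strongest case against is that 4.5.1 does not say any grade; that is inferred from its silence. The neighbouring bullets supply a natural threshold, sections 3.1.5 and 6.1.4 speak of treatment until unacceptable toxicity, and section 5.3.2.5 allows dosing with laboratory values of Grade 2 or less. This stands as a reason for caution at Grades 1–2. It does not resolve derazantinib at the higher grades.

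Second, the bullet concerns adverse events, and sections 5.3.2.5 and 7.4.3.1.1 say an abnormal laboratory value is not recorded as one unless it is clinically relevant or meets stated criteria. This stands too: an isolated Grade 1 ALT rise will often not trigger the bullet and is a poor example.

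Third, section 6.1.2.6 already refers to 4.5.1, so it is not simply opposed to it. That is correct, but the reference does not say whether the Investigator's discretion over derazantinib survives when attribution is unclear.

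Fourth, there are other routes. Section 6.1.1.5 sends dose questions to the Medical Monitor, section 1.4.3.2 points to current checkpoint-inhibitor guidelines, and Appendix 4 is a shortened form of Investigator's Brochure guidance not available here. These may help in a given case. None of the text available ranks 4.5.1 against Table 5.

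**Conclusion.** The contradiction holds within limits: derazantinib at Grades 1–3 and atezolizumab at Grades 1–2, clearest for derazantinib at Grade 3 hepatic and Grade 2–3 retinal events. It rests on the assumption that an unattributable event is normally rated at least possibly related to each drug. The rule could reach 36 + 50 = 86 planned evaluable combination patients if Substudy 3 and Cohort 4b run to full size, plus crossover patients. That is the population under the rule, not the number affected.

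A reader might infer more than the documents support:

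- **That the rules conflict at every grade, or that sites will act in opposite ways.** They agree at Grade 4, and for atezolizumab at Grade 3. Different handling is possible, not certain.
- **That unclear attribution will be the usual case.** No frequency is given. Among the 26 Substudy 2 patients there were no dose-limiting toxicities, and the only immune-related event reported was one nephritis.
- **That Substudy 3 or Cohort 4b loses power.** The documents give no share of responders lost this way. A response already confirmed stands, and patients who stop without radiologic progression should be imaged where possible.
- **That the comparison of Cohorts 4a and 4b is biased.** The cohorts are declared non-comparative and comparisons are descriptive. More stopping on two drugs may be part of that regimen's effect.

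**What to change.** Reconcile section 4.5.1, Table 5, section 6.1.2.6 and Appendix 4. For a hepatic or ocular event possibly due to both drugs, state at each CTCAE grade which passage governs each drug. State also whether discontinued in the overlapping-toxicity bullet means temporarily or permanently, and whether the limits in the neighbouring bullets apply to it. Cross-reference that one rule from all four places; section 6.1.2.6 already points to 4.5.1, so that link needs completing rather than creating. The content of the rule is for the sponsor's safety team, and no view is taken here on which passage is right. The cost is a protocol clarification and a memo to sites, with no new assessments.

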4.5.2 Patient discontinuation from the study

Patients who discontinue from study treatment will be followed for survival until the end of the study criteria are met (see Section 3.1.8), either through direct contact with the patient or the patient's relatives, or collection of public records (e.g., death certificate) in accordance with local laws, unless they meet any of the following criteria:

- Withdrawal of consent for study treatment including safety and survival follow up
- Withdrawal of consent for long-term (survival) follow-up
- Lost to follow-up
- Death

4.5.3 Replacement of patients

Patients who are non-evaluable for efficacy (see Section 8.2.2) are to be replaced.

4.5.4 Study discontinuation

The Sponsor reserves the right to temporarily or permanently discontinue the cohort, substudy or study at any site or at any time. Reasons for study discontinuation may include, but are not limited to, the following:

- Safety concerns (i.e. an identified risk or potential risk that could have an impact on the risk-benefit balance of the product or have implications for public health)
- Poor enrollment
- Non-compliance with the protocol, Good Clinical Practice (GCP) guidelines, or other regulatory requirements by the Investigator(s)
- Request to discontinue the study by regulatory or health authority

The Sponsor and/or designee will promptly inform all Investigators and the appropriate regulatory authorities if the study is suspended or terminated for safety reasons. In the case of such a termination, the Investigator will notify the IRB or Independent Ethics Committee (IEC), as appropriate.

5 SCHEDULE OF ASSESSMENTS AND PROCEDURES

Effective Protocol Version 5.0, only assessments and procedures applicable to active substudies are provided in this section.

5.1 Summary of schedule of assessments

Study patients will be assessed in accordance with the items and schedules provided in [Table 1](#). All applicable assessments must be documented in the eCRF for each patient.

Patients will be closely monitored for safety and tolerability throughout the study. Patients should be assessed for toxicity prior to the start of each cycle; and study drug dosing should occur only if the clinical assessment and local clinical safety blood test values are acceptable.

Table 1 Schedule of assessments

Assessment window	PSV	SV	Cycle 1			Cycle 2+			End of Treatment ≤ 7 days after last dose	Safety Follow-Up		Overall Survival Follow-Up At least every 3 months from date of last dose (±14)
			D1	D8 (±3)	D15 (±3)	D1 (+3) ¹	D8 ² (±3)	D15 ² (±3)		28 days after last dose (±3)	90 days after last dose (±3) ³	
Substudy applicability	S1/S3/S5	All	All	SIAP S3/S5	All	All	SIAP S3/S5	SIAP S3/S5	All	All	S3/S4	All
Informed Consent on Pre-screening ICF	X											
Molecular eligibility ⁴	X											
Informed Consent on Study ICF		X										
Screening procedures ⁵		X										
Physical examination		X	X			X			X	X	X	
ECOG PS		X	X	X	X	X	X	X	X	X	X	
Ophthalmological examination ⁶		X				X			X			
ECG ⁷		X	X	X	X	X	X	X	X	X	X	
Clinical safety laboratory blood samples ⁸		X	X	X	X	X	X	X	X	X	X	
Urinalysis ⁹		X	X			X			X			
Pregnancy test ¹⁰		X	X			X			X	X	X	
Research liquid biopsy ¹¹		X				X			X			
Archival tumor tissue ¹²		X										
Tumor imaging assessment ¹³		X				X			X			
Treatment assignment/Randomization			X									
Study drug administration			X	X ¹⁴	X ¹⁴	X	X ¹⁴	X ¹⁴				
Study drug dispensing and/or accountability			X			X			X			
Derazantinib PK ¹⁵			X	X	X	X	X	X		X		
Atezolizumab PK and ADA ¹⁶			X			X				X		
AE assessments		X ¹⁷	X	X	X	X ¹⁸	X	X	X	X	X	
PRO assessments (not S2) ¹⁹			X			X			X			
Concomitant medications/treatments		X	X	X	X	X	X	X	X	X	X	
Pharmacodynamic research (optional) ²⁰		X				X						
Survival contact ²¹											X	X

Abbreviations: ADA: anti-drug antibodies; AE: adverse event; C: cycle; D: day; ECG: electrocardiogram; ECOG PS: Eastern Cooperative Oncology Group Performance Status; PK: pharmacokinetics; PRO: patient reported outcome; PSV: Pre-screening visit; S[n]: Substudy [number]; SIAP: safety interim analysis patients; SV: Screening visit.

For footnotes, see next page.

1. Deviations from the visit schedule by +3 days are permitted for reasons other than toxicity, e.g., for administrative reasons or to accommodate travel logistics. If a patient visit deviates from the permitted protocol window, the next visit must be performed at the correct timing based on the date of C1D1.
2. Only applicable to Cycle 2.
3. Applicable to all patients who received atezolizumab as part of their study treatment.
4. Applicable to **Substudies 1, 3 and 5** only (see Section 3.1.1).
5. Screening procedures (see Section 5.2.1.3) comprise assessment of eligibility criteria; medical history of cancer diagnosis and treatment; demographics, medical history, prior medications, baseline medical conditions, including weight and height; Bellmunt score assessment, tuberculosis blood test (e.g., interferon- γ release assay) if clinically indicated to rule out clinical suspicion of active tuberculosis; serology for human immunodeficiency virus, hepatitis B, and hepatitis C.
6. Patients will have complete ophthalmological examination, including optical coherence tomography (OCT), during Screening, the first four cycles (i.e., Day 1 [\pm 7d] of Cycles 2–5) and the End of Treatment visit. A complete ophthalmological examination is to be repeated if new ocular symptoms occur or vision is impaired (see Section 5.3.2.3).
7. For all patients, a standard, triplicate, 12-lead ECG must be performed and read locally at all study visits; central reading of all ECG results will be performed (see Section 5.3.2.4). Note that the on-treatment ECGs (up to Cycle 4) should be performed as close as possible to the corresponding PK blood collection timepoint during those visits (see Footnote 16); if possible, ECG should be performed first, and then blood collected for PK within 5–10 minutes. Subsequently, ECGs will be performed pre-dose on Day 1 of every cycle, at End of Treatment and at Safety Follow-up.
8. Safety laboratory blood samples will be tested locally at all study visits. The results of these assessments must be reviewed prior to dosing (see Section 5.3.2.5).
9. Comprising specific gravity, pH, glucose, protein, ketones, and blood (see Section 5.3.2.6).
10. Women of child-bearing potential must have a negative local serum pregnancy test (hCG) at the SV and within 72 hours prior to dosing at C1D1. Subsequently, serum pregnancy testing will be performed prior to study drug dosing on Day 1 of every cycle, at the End of Treatment visit, and serum or urine pregnancy testing will be performed monthly for 150 days (5 months) following the last administration of study treatment. Monthly pregnancy testing after the end of treatment may be performed by the patient's local gynecologist to reduce the burden related to study visits at the site, but must be communicated to the study Investigator.
11. Research liquid biopsies are requested from all patients enrolled in **Substudies 1, 3, 4 and 5** at Screening and End of Treatment visits, and at the time point of the confirmatory CT scan (for complete response/partial response).

12. Archival tumor tissue (FFPE block; or a minimum of two H&E-stained slides plus at least 10 consecutive, unstained, $4 \pm 1 \mu\text{m}$ thick sections, placed on positively charged slides) should be collected at the SV from **all enrolled patients** for biomarker assessment (including PD-L1 testing). If archival tumor tissue is not available, *de novo* biopsy may be performed but only if considered by the Investigator as safe and tolerable for the patient.
13. Tumor assessments performed as SoC prior to obtaining informed consent and within 28 days of the first dose of study treatment on C1D1 may be used rather than repeating tests. The first on-study tumor imaging assessments will be performed after 9 weeks on study, and will be repeated every 9 weeks (± 7) from C1D1 (i.e., at C4D1, C7D1, C10D1) and every 12 weeks (± 7) from C10D1 (i.e., at C14D1, C18D1, etc.) thereafter (with additional scans as clinically indicated and as per RECIST 1.1 criteria) until disease progression, death, or loss of follow-up. A tumor assessment should be performed at the End-of-Treatment visit only if the prior scan was not done within 4 weeks (28 days) prior to this visit, or if the prior scan did not show radiographic disease progression (see Sections 5.2.2.7 and 5.3.3.2). The same radiographic procedure as used at the SV must be used throughout the study for each patient to follow target lesions, and results must be reviewed by the Investigator before dosing at the next cycle. Imaging timing should be based on the first dose at C1D1, should follow calendar days, and should not be adjusted for delays in cycle starts.
14. For pre-dose PK blood sampling at C1D15 (**all substudies**), and C1D8, C2D8 and C2D15 (**safety interim analysis patients in Substudies 3 and 5**), administer derazantinib at the study site.
15. Derazantinib PK blood (plasma) sampling will be performed according to the following schedule:
 - a. **Rich PK profiling - Applicable to safety interim analysis patients in Substudy 3 and 5 only:**
 - C1D1, prior to derazantinib dose, and 1 hour (± 5 minutes), 2 hours (± 5 minutes), 4 hours (± 15 minutes), 8 hours (± 30 minutes), 10 hours (± 30 minutes), 12 hours (± 30 minutes; prior to the second dose administration), 24 hours after first derazantinib administration (i.e., 12 hours post second dose administration but within 1 hour prior to the third dose).
 - C1D8, pre-dose (within 1 hour prior to the next dose), and 6–8 hours after derazantinib administration.
 - C1D15, pre-dose (within 1 hour prior to the next dose), and 6–8 hours after derazantinib administration.
 - C2D1, prior to derazantinib (within 1 hour prior to the next dose), and 1 hour (± 5 minutes), 2 hours (± 5 minutes), 4 hours (± 15 minutes), 8 hours (± 30 minutes), 10 hours (± 30 minutes), 12 hours (± 30 minutes; prior to the second dose administration), 24 hours after derazantinib administration (i.e., 12-hour post previous dose administration but within 1 hour prior to the next dose).
 - C2D8, pre-dose (within 1 hour prior to the next dose), and 6–8 hours after derazantinib administration.
 - C2D15, pre-dose (within 1 hour prior to the next dose), and 6–8 hours after derazantinib administration.
 - C3D1, prior to derazantinib (within 1 hour prior to the next dose), and 6–8 hours after derazantinib administration.
 - C4D1, prior to derazantinib administration (within 1 hour prior to the next dose).
 - 28-day Safety Follow-up visit
 - b. **Sparse PK – Applicable to all patients (except safety interim analysis patients in Substudy 3 and 5; see rich PK sampling):**
 - C1D1 and C1D15, prior to derazantinib (within 1 hour prior to next dose), and 6–8 hours after the study drug administration.

- C2D1, prior to derazantinib (within 1 hour prior to next dose)
 - C3D1, prior to derazantinib (within 1 hour prior to next dose), and 6–8 hours after the study drug administration.
 - C4D1, prior to derazantinib administration (within 1 hour prior to next dose)
 - 28-day Safety Follow-up visit
16. For all patients in **Substudy 3** and **Cohort 4b and Crossover**, atezolizumab PK and ADA (serum) blood sampling will be performed according to the following schedule:
- C1D1, prior to atezolizumab administration; and for PK only, 30 minutes after end of atezolizumab infusion
 - C2D1, C3D1, C4D1, prior to atezolizumab administration
 - C8D1, C12D1, C16D1, prior to atezolizumab administration
 - 28-day Safety follow-up visit
17. Non-serious and serious changes in or worsening of a patient’s condition that occur between any informed consent and first study-drug administration, as well as any AEs in conjunction with tumor/liquid biopsies or imaging studies, will be captured in the eCRF (see Section 7.4.2).
18. AEs occurring between C1D1 and C1D21 in patients during the DLT observation period of **Substudy 3 and 5** will be assessed against the DLT definitions (outlined in Section 7.3.3) prior to study drug administration on C2D1. DLTs are also to be recorded in the eCRF.
19. PRO instruments should be self-administered at the study site before the patient sees the physician (i.e., at the start of the visit) and prior to the completion of other study assessments and the administration of study treatment (see Section 5.3.6).
20. (*Optional*) PD assessments in Substudy 3, 4 or 5 (i.e., blood sampling and skin biopsy) to be performed at screening, and on C2D1.
21. Survival contact can be in person, via phone, or, where applicable, by checking regional/national death registries.

